## 1.0 INVESTIGATIONAL PLAN SUMMARY

### 1.1 Study Purpose

The purpose of this randomized pivotal study is to evaluate the safety and efficacy of the EPi-Sense®-AF Guided Coagulation System with VisiTrax® to treat symptomatic persistent Atrial Fibrillation (AF) patients who are refractory or intolerant to at least one Class I and/or III AAD. For the purposes of this study:

Refractory to Class I and/or III AAD will be defined as drug used that did not result in the absence of AF or atrial flutter (AFL);

Intolerant to Class I and/or III AAD will be defined as drug that patient was unable to tolerate and/or the side effects listed in the manufacturer's instructions for use were observed in the patient during the AAD drug therapy.

Persistent AF will be defined according to the Heart Rhythm Society (HRS) "HRS 2012 Expert Consensus Statement on Catheter and Surgical Ablation of AF".

- Persistent AF is defined as continuous AF that is sustained beyond 7 days. Episodes of AF in which a decision is made to electrically or pharmacologically cardiovert the patient after  $\geq$ 48 hours of AF, but prior to 7 days, should also be classified as persistent AF episodes.

Persistent AF to be documented by:

- Physician notes in patient's medical history **AND**
- Two ECGs (from any forms of rhythm monitoring) showing continuous AF with ECGs taken at least 7 days apart, within last 12 months. **OR**
- History of failed DC cardioversion (electrical or pharmacologic)

It is anticipated that the data from this randomized pivotal clinical study will be used to support a premarket approval application (PMA) to obtain Food and Drug Administration (FDA) approval to market the EPi-Sense®-AF Guided Coagulation System with VisiTrax® for the treatment of symptomatic persistent AF in patients who are refractory or intolerant to at least one Class I and/or III AAD.

### 1.2 Name and Intended Use of Device

Common Name:	Surgical Device for Ablation of Cardiac Tissue
Trade Name:	EPi-Sense®-AF Guided Coagulation System with VisiTrax®
Intended Use:	The EPi-Sense-AF Guided Coagulation System with VisiTrax is intended for the treatment of symptomatic persistent Atrial Fibrillation that is refractory or intolerant to at least one Class I and/or III anti-arrhythmic drug (AAD) when used with an open irrigated RF ablation catheter to complete PV isolation by ablating breakthroughs between the epicardial lesions.

### 1.3 Study Design

This is a, prospective, open label 2:1 randomized (convergent procedure versus standalone endocardial catheter ablation) multi-center pivotal clinical study. The study will enroll and randomize one hundred and fifty three (153) patients from up to thirty (30) sites, twenty-seven (27) US and three (3) OUS.

Potential subjects with symptomatic persistent AF will be screened by the sites for study participation. Consented subjects meeting all inclusion / exclusion criteria will be enrolled and randomized into the study.

Subjects in both arms of the study will be evaluated post procedure at 1 month, 3 months, 6 months and 12 months with a long-term follow-up visit at 18 months and long-term phone follow-up at 2, 3, 4, 5 years as detailed in this protocol. Submission for premarket approval will be filed after study subjects in both arms of the study complete the one year post procedure follow-up visit.

Annual reports will be submitted to the Agency in compliance with FDA regulatory requirements. One month safety data for the first 50 subjects in the treatment arm will be submitted to the FDA for review. During the conduct of this randomized study, any reported death, pericardial effusion leading to therapeutic drainage, atrio-aesophageal fistula or stroke will be reported to the Agency within 10 days.

#### **1.4 Study Objectives**

The objective of this clinical study is to evaluate the safety and efficacy of the EPi-Sense-AF Guided Coagulation System with VisiTrax for the treatment of symptomatic persistent AF as compared to a standalone endocardial catheter ablation.

##### **1.4.1 Primary Objectives**

To demonstrate superiority of the convergent procedure (experimental) compared to the standalone endocardial catheter ablation (control) on overall success, defined as freedom from AF/AFL/AT absent class I and III AADs except for a previously failed class I or III AAD with no increase in dosage following the 3 month blanking period through the 12 months post procedure follow-up visit.

The incidence rate of Major Adverse Events (MAEs) in the treatment arm will demonstrate an acceptable risk profile.

##### **1.4.2 Secondary Objectives**

To demonstrate the efficacy of the procedure as a 90% reduction in the subject's baseline AF burden at 12 months post procedure in the presence or absence of class I / III AADs and a change in QOL measures and the six minute walk test scores from the baseline to 12 months post procedure.

##### **1.4.3 Exploratory Objectives**

To demonstrate the efficacy of the procedure as a 90% reduction in the subject's baseline AF burden at 18 months post-procedure in presence or absence of Class I/III AAD's.

To explore the impact of the convergent procedure on left atrial size and left ventricular ejection fraction. In addition we may evaluate the number of hospitalizations, total number of days hospitalized, and number of rhythm disturbance treatments for a period of 12 months before and after the convergent procedure for a health economics data analysis.

#### **1.5 Study Endpoints**

##### **1.5.1 Primary Efficacy Endpoints**

The primary efficacy endpoint is success or failure to be AF/AT/AFL free absent class I and III AADs except for a previously failed or intolerant class I or III AAD with no increase in dosage following the 3 month blanking period through the 12 months post procedure follow-up visit.

The results of the holter data used for the primary efficacy endpoint evaluation will be evaluated by an independent reviewer thus maintaining the objectivity of the primary efficacy endpoint.

Subjects will be considered primary efficacy failures if any of the following conditions are observed:

- Any electrocardiographically documented AF/AFL/AT episode of 30 sec duration or longer by Holter, event monitor or rhythm strip; or for the full 10 second recording of a standard 12 lead ECG following the 3 month blanking period through the 12 months post procedure follow-up visit.
- The use of a new or an increase in the dose of a previously failed class I or class III AAD following the 3 month blanking period through the 12 months post procedure follow-up visit.
- DC cardioversion for AF/AFL/AT following the 3 month blanking period through the 12 months post procedure follow-up visit.
- Subsequent left-sided catheter ablation for AF/AFL/AT at anytime during the 12 months post procedure follow-up visit.
- Catheter ablation for right-sided typical atrial flutter following the 3 month blanking period through the 12 months post procedure follow-up visit.

### **1.5.2 Secondary Efficacy Endpoints**

The secondary efficacy endpoints are:

- Success or failure to achieve a 90% reduction from baseline AF burden and off all Class I and III AADs at 12 months post procedure
- Success or failure to achieve a 90% reduction from baseline AF burden regardless of their Class I and III AAD status at 12 months post procedure
- Change in QOL measures at 12 months post procedure from baseline values
- Change in 6 minute walk test score from baseline score
- Success or failure to be AF free and off all Class I and III AADs except a previously failed or intolerant Class I or III AAD with no increase in dosage following the 3 month blanking period through the 12 months post procedure follow-up visit
- Success or failure to be AF free regardless of Class I and III AAD status following the 3 month blanking period through the 12 months post procedure follow-up visit.

### **1.5.3 Primary Safety Endpoint**

The primary safety endpoint for the study will be defined as the incidence of major adverse events (MAEs) listed below for subjects undergoing the convergent procedure for the procedural to 30 day post procedure time period.

All MAEs will be adjudicated by the Clinical Events Committee (CEC), thus maintaining the objectivity of the primary safety endpoint.

- Cardiac tamponade/perforation: is defined as the development of a significant pericardial effusion during or within 30 days of undergoing an AF ablation procedure. A significant pericardial effusion is one which results in hemodynamic compromise, requires elective or urgent pericardiocentesis, and results in a 1 cm or more pericardial effusion as documented by echocardiography. Cardiac tamponade/perforation should also be classified as “early” or “late” depending on whether it is diagnosed during or following initial discharge from the hospital.  
Documentation of CT Scan/MRI/ECHO findings and subsequent treatment such as thoracentesis or pericardiocentesis.
- Severe Pulmonary vein (PV) stenosis: Narrowing of the pulmonary veins. PV stenosis can be categorized as mild (<50%), moderate (50–70%), and severe (≥70%) reduction in the diameter of the PV or PV branch. Severe PV stenosis should be considered a major complication of AF ablation.  
Documentation by CT or MRI scan of ≥70% vessel narrowing compared to the baseline.
- Excessive Bleeding: is defined as a major complication if it is subsequent to a device related or study procedure-related injury and is treated with transfusion or results in a 20% or greater fall in HCT. Transfusion for anemia or other pre-existing conditions

that cause a fall in HCT without acute bleeding will not be considered a Major Adverse Event.

Documentation of the cause of the bleed, and transfusion, and/or 20% or greater drop in HCT.

- Myocardial infarction (MI): When low blood flow causes the heart to starve for oxygen. Heart muscle dies or becomes permanently damaged.

Documentation of MI; the presence of any one of the following criteria: (1) detection of ECG changes indicative of new ischemia (new ST-T changes or new LBBB) which persist for more than 1 h, (2) development of new pathological Q waves on an ECG, and (3) imaging evidence of new loss of viable myocardium or new regional wall motion abnormality.

- Stroke: A stroke is an interruption of the blood supply to any part of the brain. Rapid onset of a focal or global neurological deficit with at least one of the following: change in level of consciousness, hemiplegia, hemiparesis, numbness or sensory loss affecting one side of the body, dysphasia or aphasia, hemianopia, amaurosis fugax, or other neurological signs or symptoms consistent with stroke.

Duration of a focal or global neurological deficit  $\geq 24$  h; OR  $< 24$  h if therapeutic intervention(s) were performed (e.g., thrombolytic therapy or intracranial angioplasty); OR available neuroimaging documents a new hemorrhage or infarct; OR the neurological deficit results in death AND no other readily identifiable non-stroke cause for the clinical presentation (e.g., brain tumor, trauma, infection, hypoglycemia, peripheral lesion, pharmacological influences).

Diagnosis should be confirmed by a neurology or neurosurgical specialist utilizing a neuroimaging procedure (MR or CT scan or cerebral angiography) or lumbar puncture (i.e., spinal fluid analysis diagnostic of intracranial hemorrhage).

Documentation of a stroke or CVA consisting of acute loss of neurological function caused by an ischemic event with residual symptoms at least 24 hours after onset confirmed by CT or MRI scan or cerebral angiography of acute neurological event.

- Transient Ischemic attacks (TIA): A transient ischemic attack is a "mini-stroke" caused by temporary disturbance of blood supply to an area of the brain, which results in a sudden, brief decrease in brain function. Clinical symptoms similar to stroke but last for less than 24 hours.

Documentation of TIA neuroimaging without tissue injury consistent with acute loss of neurological function caused by an ischemic event with resolution of symptoms within 24 hours after onset.

- Atrioesophageal fistula: An atrioesophageal fistula is defined as a connection between the atrium and the lumen of the esophagus.

Documentation of an atrial-esophageal fistula: A CT or MRI scan and documentation of esophageal erosion combined with evidence of a fistulous connection to the atrium such as air emboli, an embolic event, or direct observation at the time of surgical repair.

- Phrenic Nerve Injury: Injury to the phrenic nerve that may be caused during the surgical procedure to access the heart or during ablation (epicardial or endocardial).

Documentation of clinical signs or symptoms for phrenic nerve injury such as paralysis of the diaphragm on one or more sides confirmed by fluoroscopy or a chest X-ray.

- Death: Document cause of death and include autopsy findings if autopsy performed.

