#### **6.2 7 Day post procedure Visit (7 days +7 days post index procedure)**

After completion of the study procedure subjects in both study arms will return for a post procedure follow-up visit at 7 days for an evaluation of any peri-procedural adverse symptoms. The 7 days post procedure evaluation will include:

- Evaluation of any adverse events
- Evaluation of any major adverse events (MAEs)
- Medications – Class I and III AADs, other cardiac medications and anticoagulants
- Trans Thoracic ECHO (TTE) to evaluate for any effusions
- Schedule subject for 1 month visit.

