## 8.0 ADVERSE EVENTS

Safety data for the primary safety endpoint will be collected from the start of the coagulation procedure to 30 days post procedure. The primary safety endpoint will be an evaluation of the incidence of major adverse events (MAE) listed below for the procedural to 30 day post procedure time period, for each arm of the study.

The secondary safety endpoint for the study will be an analysis of the incidence of major adverse events, in each arm of the study, from 30 days post procedure through the 12 months post procedure visit, for each arm of the study.

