### 8.1 Major Adverse Events (MAE)

Events qualifying as MAEs as defined in 1.5.4 include:

- Cardiac tamponade/perforation requiring pericardiocentesis or thoracentesis
- Severe Pulmonary Vein Stenosis ( $\geq 70\%$  occlusion)
- Excessive bleeding requiring transfusion or  $> 20\%$  drop in HCT.
- Myocardial infarction
- Stroke
- Transient Ischemic Attacks (TIA)
- Atrioesophageal fistula
- Phrenic nerve injury
- Death

Any condition that was recorded as pre-existing is not a MAE unless there is a change in the nature, severity or degree of the condition.

Sick Sinus Syndrome (SSS) and the implantation of a pacemaker for treatment of SSS post procedure will not be recorded as a MAE since it is a known underlying condition for patients with persistent AF and undergoing cardiac coagulation procedures.

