## **9.0 STATISTICAL ANALYSIS**

### **9.1 Summary Descriptive Statistics**

This randomized pivotal study plans to enroll 153 randomized subjects.

Standard descriptive statistics will be used to summarize numeric variables, including the number of observed values, mean, standard deviation, median, minimum and maximum values. Summaries of categorical variables will include the number and percentage of observed values, at each level of the categorical variable.

Baseline and demographic information, including age, gender, race, ethnicity, height, weight, BMI, and medical history will be summarized with standard descriptive statistics. Primary and secondary efficacy endpoints, including AF/AT/AFL free and Class I and III AAD status, 90% reduction in AF burden and Class I and III AAD status, and change in Quality of Life and 6 minute walk test scores will be summarized by visit. Categorical summaries will be based on the number of subjects with an available assessment. QOL measures will be summarized numerically including change from baseline and percent change from baseline to 12 months post procedure follow-up.

All safety data will be summarized descriptively and reported for the 30 days post-procedure and from 30 days to 12 months post-procedure time periods for the treatment groups.

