7.4.6 Catheter Ablation

Catheter ablation date and location(s) (as a free text field) are collected on the Rhythm Disturbance Evaluation eCRF page. Prior to database lock and subsequent unblinding of study sponsor, a list of ablation locations will be tabulated and provided to the Medical Monitor or designee for categorization of ablation location. Possible categorizations will include: Left, Right, Other, or Indeterminate. This list will not include subject identifiers or treatment arm. This information will be finalized prior to database lock, and incorporated into analysis datasets in order to determine if subjects meet criteria for treatment failure based on left or right side cardiac ablations as specified in Section 9.1.

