10.1 Major Adverse Events (MAEs)

MAEs (listed below and defined in Section 1.5.3 of the study protocol) will be adjudicated by the CEC. These adjudicated events will be recorded in a spreadsheet following the committee meeting and provided to the sponsor or designee after each meeting. The complete list of adjudicated events will be finalized prior to database lock and incorporated into an analysis dataset, separate from the adverse event dataset. MAEs will be summarized by event type and treatment arm, based on onset date:

- Date of study procedure through the 30th day post-procedure
- 31st day post-procedure through 12 months (365th day) post-procedure
- Overall

The MAEs for this study are as follows:

- Cardiac tamponade/perforation

- Severe pulmonary vein stenosis
- Excessive bleeding
- Myocardial infarction
- Stroke
- Transient ischemic attack
- Atrioesophageal fistula
- Phrenic nerve injury
- Death

The primary safety analysis will be to document an acceptable risk profile. This criterion will be defined as an acceptable level of MAEs. It is estimated that the true incidence rate for MAEs in this study population is no more than 12%. A 95% one-sided confidence interval for the investigational treatment arm based on a 102 subject sample size is 5%, resulting in an upper bound of MAEs being less than 20%. This result would document an acceptable risk profile for the investigational arm.

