10.2 Adverse Events (AEs)

All reported terms (investigator descriptions) for AEs will be coded using the Medical Dictionary for Regulatory Activities (MedDRA) version 18.0. Treatment-emergent AEs (TEAEs) will be defined as AEs starting on or after the day of the study procedure. Relationship to EPi-Sense_AF device, relationship to endocardial catheter system, and relationship to study treatment/procedure, all reported as not related, unlikely related, possibly related, probably related, or definitely related, will be categorized as related (probably, possibly, or definitely), or unrelated (unlikely or not related).

All summaries of TEAEs will be presented by event type or system organ class (SOC) (as collected on the eCRF) and, for those in 'Other' event type, by SOC, preferred term (PT), and by treatment arm. Subjects will be counted at most 1 time per event type, SOC, or PT. Events will be summarized at the maximum severity or highest reported relationship, where applicable. The following summaries will be presented:

- TEAEs
- TEAEs with onset through the 30th day after study procedure
- Treatment-emergent serious adverse events (SAEs)
- Severe TEAEs
- TEAEs leading to discontinuation from the study
- TEAEs related to study treatment/procedure
- TEAEs related to endocardial catheter system
- TEAEs related to study device
- TEAEs by severity

All AEs will be listed by subject, event type, SOC, PT, verbatim term, and onset

date. Additional listings will be provided for SAEs, AEs leading to discontinuation, AEs leading to death, and unanticipated adverse device effects (UADE).

11 **INTERIM ANALYSES**

There are no planned interim analyses. Ad hoc analyses may be performed from time to time as necessary for regulatory agencies, safety review, corporate planning, etc. No adjustments to p-values in the final analyses will be made for such ad hoc analyses.

12 **PLANNED STUDY ANALYSES**

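### The tamponade definition used for the day 31–365 and Overall MAE rows stops at 30 days after an ablation, so a later index-procedure tamponade is left out of both

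*Protocol*

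**What the plan says.** Protocol 1.5.3 defines the nine MAE types under the primary safety endpoint, whose window runs from the procedure to 30 days. Cardiac tamponade/perforation "is defined as the development of a significant pericardial effusion during or within 30 days of undergoing an AF ablation procedure". The effusion must also meet the section's criteria on haemodynamic compromise, pericardiocentesis and echocardiographic size. The definition adds an early/late label, which depends on whether diagnosis comes before or after the first hospital discharge.

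SAP 10.1 refers to Protocol 1.5.3 for all MAE definitions and has the CEC adjudicate the events. It summarises them by type, arm and onset date in three rows: procedure to day 30, "31st day post-procedure through 12 months (365th day) post-procedure", and Overall. Tamponade/perforation is one of the listed types.

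The protocol also plans for the later period. Section 8.0 calls for "an analysis of the incidence of major adverse events, in each arm of the study, from 30 days post procedure through the 12 months". Section 9.1 says: "All safety data will be summarized descriptively and reported for the 30 days post-procedure and from 30 days to 12 months post-procedure time periods". Section 8.1 lists the event with no day limit, as "Cardiac tamponade/perforation requiring pericardiocentesis or thoracentesis".

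**The concern.** The 30-day clause suits the primary safety window. SAP 10.1 carries the same definition into a window that begins the day after the clause expires. A zero in the late tamponade row could then come from the definition and not from the data, and a reader of the table could not tell which.

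The event is clinically relevant here. The post-operative management part of Protocol Attachment A recommends anti-inflammatory prophylaxis because inflammatory mechanisms can cause late pericardial effusions. It puts no day on late, so it shows relevance and not a rate. Protocol 8.5 requires drained effusions to be reported to the FDA with no 30-day limit. A drained effusion after day 30 could therefore be reported to the FDA and yet be missing from the trial's own late MAE row.

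**Working it through.** No figure in the plan is in dispute, so the check is mainly a comparison of texts.

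**Step 1: which definition governs.** SAP 10.1 cites Protocol 1.5.3, with one definition per event type for all three rows.

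**Step 2: apply it to each row.**

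| Tamponade | Meets the 1.5.3 time clause? | Day 0–30 row | Day 31–365 row | Overall row |
|---|---|---|---|---|
| Index procedure, onset by day 30 | Yes | Counted | – | Counted |
| Index procedure, onset after day 30 | No | – | Not counted | Not counted |
| Onset after day 30, within 30 days of a repeat AF ablation | Yes | – | Counted | Counted |

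**Step 3: look for text that lifts the limit.**
- The early/late label in 1.5.3 turns on hospital discharge, not on day 30.
- Protocol 8.1 omits the limit but defers to a definition elsewhere. It gives the reference as 1.5.4, which is the serious adverse event (SAE) endpoint. The SAP does not cite 8.1.
- SAP section 13 (departures from the protocol) does not mention the clause.

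**Step 4: is this specific to tamponade?** None of the other eight definitions in 1.5.3 limits the days since ablation. The hour limits for myocardial infarction, stroke and TIA concern how long findings last. So one of nine types is affected.

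**Step 5: the primary endpoint.** Its window coincides with the clause, so no event is lost. The plan's precision statement also stands: with 12% and n = 102, the one-sided 95% margin is 1.645 × √(0.12 × 0.88 / 102) = 5.3 points. The upper bound is 17.3%, in line with the stated 5% and below 20%.

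**Step 6: size per excluded case, at planned arm sizes.**
- Convergent arm: 1/102 = 0.98 percentage points.
- Control arm: 1/51 = 1.96 percentage points.

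These apply to the tamponade rows. A subject-level rate of any MAE falls by the same amount only if that subject had no other MAE in the window.

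**Step 7: range of excluded cases.** The documents give no rate of tamponade after day 30. The rates below are assumptions.

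| Assumed late rate | Convergent (× 102) | Control (× 51) |
|---|---|---|
| 0% | 0 | 0 |
| 0.5% | 0.51 | 0.26 |
| 1% | 1.02 | 0.51 |
| 2% | 2.04 | 1.02 |

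**The case against.** The strongest reply is that the exclusion follows from one reading of an inconsistent text. The clause sits under the primary safety endpoint, Protocol 8.1 omits it, MAEs are evaluated at visits through 18 months, and SAP 10.1 itself allots listed MAEs to windows through day 365. A CEC might count late cases anyway. That is possible, but the SAP names 1.5.3 as its source, and a committee following that source would reject them. If it followed 8.1 instead, the late count would depend on which text it chose, which also needs settling.

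The second reply concerns weight, and it stands. SAP section 10 tests no safety hypothesis. The secondary safety endpoint in Protocol 1.5.4 and SAP 2.3.4 is SAEs, although Protocol 8.0 gives that name to the late MAE analysis. A tamponade meeting the other criteria should qualify as an SAE and appear by arm in the SAP 10.2 summaries. A case sent to the CEC and rejected should appear in Listing 16.2.7.2. What is at risk is its count as an MAE, not the record of the event.

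The third reply is that dropping the clause after day 30 removes the only link between effusion and ablation, while bleeding and phrenic nerve injury keep a procedural link. That is a fair caution. However, myocardial infarction, stroke, TIA and death carry no such link in 1.5.3, and flagging repeat ablations and showing recorded relatedness lets a reader separate the cases.

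Finally, 102 and 51 are planned randomised numbers, not the Safety Population. The per-case figures illustrate scale and do not predict an effect.

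**Conclusion.** The concern holds. Under the definition that SAP 10.1 cites, an index-procedure tamponade starting after day 30 is excluded from the day 31–365 and Overall rows, although Protocol 8.0, Protocol 9.1 and the SAP all plan to report that period.

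The consequence is modest: a possible understatement in one of nine event types, in descriptive rows, of 0.98 points per case in the convergent arm or 1.96 in the control arm. If no such event occurs, nothing changes. The primary safety endpoint is unaffected, and no bias between arms is claimed. The conclusion rests on the CEC applying 1.5.3 as written. It is worth correcting because the rule as stated gives the wrong count and the correction is simple.

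**What to change.** State in SAP 10.1 and in the CEC instructions that the 30-day clause in the tamponade definition applies only to the primary window, procedure to day 30. For days 31 to 365 and Overall, count by onset date the CEC-adjudicated effusions that meet the remaining 1.5.3 criteria.

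Flag those within 30 days of a repeat ablation; SAP 7.4.6 confirms the dates exist: "Catheter ablation date and location(s) (as a free text field) are collected on the Rhythm Disturbance Evaluation eCRF page". Show attribution from the fields that SAP 10.2 already reports, including "relationship to endocardial catheter system, and relationship to study treatment/procedure", so that no new CEC judgement is needed. Review any late effusion in Listing 16.2.7.2 that was rejected on the 30-day clause.

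The cost is one SAP sentence, one CEC instruction and a link between the MAE and adverse event datasets, which SAP 10.1 keeps separate. No visits or forms are added. Ascertainment stays limited: Protocol 6.2 schedules a "Trans Thoracic ECHO (TTE) to evaluate for any effusions" at 7 days, and the only later scheduled TTE in the first year is at 6 months. Late cases would come mainly from adverse event reports and clinical echocardiography. The downside for the sponsor is that the late MAE rate may look slightly less favourable.

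### The primary safety definition in Protocol 1.5.3 requires hemodynamic compromise, drainage and 1 cm together for a tamponade/perforation event, while Protocol 8.1 qualifies the same event by drainage; the two must be reconciled

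*Protocol*

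**What the plan says.** **Definition.** Protocol 1.5.3 builds the cardiac tamponade/perforation MAE on a significant pericardial effusion, and says of it: "A significant pericardial effusion is one which results in hemodynamic compromise, requires elective or urgent pericardiocentesis, and results in a 1 cm or more" effusion on echocardiography. The documentation line below it asks for something different: "Documentation of CT Scan/MRI/ECHO findings and subsequent treatment such as thoracentesis or pericardiocentesis".

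**List of qualifying events.** Protocol 8.1 gives the same MAE as "Cardiac tamponade/perforation requiring pericardiocentesis or thoracentesis". The list is introduced by "Events qualifying as MAEs as defined in 1.5.4 include". Section 1.5.4 is the secondary safety endpoint on serious adverse events and defines no MAE.

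**Which text governs.** SAP 10.1 says "MAEs (listed below and defined in Section 1.5.3 of the study protocol) will be adjudicated by the CEC", and SAP 2.3.3 makes the same reference. The SAP's own list gives only the label of each event.

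**FDA reporting.** Protocol 1.3 says "any reported death, pericardial effusion leading to therapeutic drainage, atrio-aesophageal fistula or stroke will be reported to the Agency". Protocol 8.5 repeats the drainage criterion.

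**Stroke.** The 1.5.3 definition is met, among other routes, if "available neuroimaging documents a new hemorrhage or infarct". The documentation line for the same item reads "Documentation of a stroke or CVA consisting of acute loss of neurological function caused by an ischemic event with residual symptoms", and it sets a 24-hour minimum for those symptoms.

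**Acceptance criterion.** Protocol 9.7 and SAP 10.1 assume a true MAE rate of no more than 12%. They give a one-sided 95% interval of 5% at 102 subjects, and call the risk profile acceptable if the upper bound is below 20%.

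**The concern.** The three conditions in 1.5.3 stand in one list joined by *and*. An adjudicator who follows the text would reject an effusion that was drained in a hemodynamically stable subject. One who opens 8.1 could accept it. A primary endpoint should not depend on which section is read.

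Effusion is a complication that the protocol itself plans for in the convergent arm. Attachment A leaves a pericardial drain in place and gives advice aimed at late inflammatory effusions. Section 6.2 schedules a transthoracic echo at the 7-day visit to look for effusions. A scheduled echo can find an effusion before it causes compromise, and those are the cases that the literal wording leaves out. The primary safety claim rests on a count of MAEs against a fixed bound, so each case left out works in favor of the device.

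**Working it through.** **1. The criteria side by side**

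| Place | Hemodynamic compromise | Drainage or treatment | 1 cm or more |
|---|---|---|---|
| Protocol 1.5.3, definition | required | pericardiocentesis required | required |
| Protocol 1.5.3, documentation line | not mentioned | treatment, with thoracentesis or pericardiocentesis as examples | imaging findings, no threshold |
| Protocol 8.1 | not mentioned | pericardiocentesis or thoracentesis | not mentioned |
| Protocol 1.3 and 8.5 (FDA reporting) | not mentioned | therapeutic drainage | not mentioned |

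Every event that meets the 1.5.3 definition also meets the 8.1 criterion, but not the reverse. The literal 1.5.3 reading can therefore only give an equal or lower count.

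**2. A test case.** Take an effusion seen on the 7-day echo and drained electively while the subject is stable. It goes to the FDA under 1.3 and 8.5, and it fits the 1.5.3 documentation line. It fails the 1.5.3 definition for want of hemodynamic compromise.

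**3. The plan's own figure.** Inputs from Protocol 9.7: p = 0.12, n = 102, one-sided 95% (z = 1.645).

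Half-width = 1.645 × √(0.12 × 0.88 / 102) = 5.29%, which rounds to the stated 5%. Upper bound = 12% + 5.29% = 17.3%, below 20%. The figure reproduces with the normal approximation.

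**4. The margin in subjects.** One subject is 1/102 = 0.98 percentage points. With p = k/102:

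- normal approximation: p + 1.645 × √(p(1 − p)/102)
- exact (Clopper-Pearson): the 95th percentile of Beta(k + 1, 102 − k)

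| Subjects with an MAE (k) | Rate | Normal bound | Exact bound |
|---|---|---|---|
| 12 | 11.8% | 17.0% | 18.4% |
| 13 | 12.7% | 18.2% | 19.5% |
| 14 | 13.7% | 19.3% | 20.6% |
| 15 | 14.7% | 20.5% | 21.7% |

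The largest passing count is 13 by the exact method and 14 by the normal approximation. From an assumed 12 counted subjects, two further subjects cross 20% by the exact method, and three by the normal approximation. If the true rate were 12%, the binomial chance of meeting the criterion would be 66% (13 or fewer) or 76% (14 or fewer), so there is not much slack at the stated ceiling.

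**5. Stroke.** The definition accepts hemorrhage. It also accepts a deficit under 24 h that was treated or that shows a new lesion on imaging. The confirmation sentence even allows a lumbar puncture diagnostic of intracranial hemorrhage. The documentation line covers only ischemic events with residual symptoms at 24 h or more. The TIA documentation line requires imaging without tissue injury and resolution within 24 h. A hemorrhagic stroke, or an imaging-positive deficit that resolves within 24 h, therefore fits neither documentation line.

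**The case against.** **8.1 may be shorthand.** Its entry still begins with cardiac tamponade/perforation and refers elsewhere for the definition. A reader might infer that 8.1 makes every drained effusion an MAE; its text does not go that far. This stands, and it softens the contradiction. It does not remove it, because the two places still differ on hemodynamic status, on the 1 cm threshold and on thoracentesis, and the section that 8.1 cites contains no definition.

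**The governing text is known.** The SAP names 1.5.3 twice. That also stands, but it means the narrow wording is the one that will be applied.

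***Or* may have been meant.** A reader might infer this because elective drainage sits awkwardly with compulsory hemodynamic compromise. The documents do not say so. The words elective and urgent describe the timing of drainage, and nothing states that compromise excludes a scheduled drainage. With *or*, every effusion of 1 cm or more would count even if never drained, against both 8.1 and the 1.5.3 documentation line.

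**The events stay visible.** Drained effusions go to the FDA. SAP Listing 16.2.7.2 shows potential MAEs that the Clinical Events Committee (CEC) rejected. SAP 10.2 tabulates adverse events through day 30 and serious adverse events by arm. An injury-related bleed with transfusion or a 20% hematocrit fall is an MAE in its own right. All of this is true, so nothing is hidden. But none of these outputs is the primary safety count, and the bleeding item would not catch an inflammatory effusion.

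**Stroke is partly protected.** Its definition is explicit about alternatives, and the narrower text is only a documentation line. That is fair, and it makes the stroke point one of alignment.

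**Conclusion.** The inconsistency is real and sits in the primary safety endpoint. Taken literally, the governing definition leaves out an effusion drained in a stable subject, although 8.1, the 1.5.3 documentation line and the FDA reporting rule all turn on treatment or drainage. The direction is certain: the literal reading cannot raise the MAE rate.

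The size is not known. No passage gives an expected number of such effusions, and 12% is stated as a ceiling, not as an expected rate. The two-or-three-subject margin rests on three assumptions: 12 of 102 subjects already counted, additional effusions only in subjects with no other MAE, and the interval method, which the documents do not name. A reader might infer that the safety conclusion would fail under a drainage-based definition. The documents do not support that; they show only that a few subjects could decide it if the count is near 12.

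**What to change.** 1. Reconcile Protocol 1.5.3 and 8.1 into one endpoint definition before the adjudicated list is finalized. State explicitly whether an effusion requiring drainage counts irrespective of hemodynamic status, as the 8.1 wording and the 1.5.3 documentation line indicate. State also whether the 1 cm threshold applies and how thoracentesis is treated.
2. Do not make the change by swapping *and* for *or*.
3. Correct the reference in 8.1 from 1.5.4 to 1.5.3. SAP 2.3.3 and 10.1 already point to 1.5.3 and need no new reference.
4. Re-read any effusion events already adjudicated under the present text.
5. Separately, align the stroke documentation line with the stroke definition, so that hemorrhage and deficits under 24 h that were treated or are imaging-positive can be documented as strokes.

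The cost is protocol wording, matching instructions to the CEC, and the re-reading. The sample size and analysis method do not change, and the change concerns how events are classified, not how patients are managed. The downside is that the reported MAE rate may rise.
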